7.1 DEMOGRAPHIC AND OTHER BASELINE CHARACTERISTICS

Descriptive summaries of the following demographic variables and characteristics measured at baseline will be presented, to include: sex, race and ethnicity, age (years) (continuous and categories), height (cm), weight (kg) (continuous and categories), BMI (kg/m²) (continuous and categories), systolic BP (mmHg), diastolic BP (mmHg), pulse rate (bpm), country and region.

In addition, the overall baseline NAS and 3 NAS sub-scores, the baseline fibrosis stage and the time since NASH diagnosis will be summarised.

Summaries of demographic data and baseline characteristics will be presented on the TS using both planned maintenance treatment and actual maintenance treatment.

7.2 CONCOMITANT DISEASES AND MEDICATION

Only descriptive statistics are planned (number and percentage of patients). Summaries of concomitant diseases (medical history and baseline conditions), concomitant medication and concomitant non-drug therapy will be based on the TS, and will all use both of actual maintenance treatment and planned maintenance treatment.

Baseline conditions and concomitant non-drug therapies will be coded according to the most recent version of MedDRA at the time of final DBL. This will include coding of trial-specific recording of medical history (“Medical History – Specific Conditions” eCRF page) for the relevant summary table (see below).

Concomitant medications will be coded according to the most recent version of the World Health Organisation (WHO) Drug Dictionary at the time of final DBL.

Baseline conditions and medical history will be summarised descriptively by MedDRA system organ class (SOC) and preferred term (PT), which will include coded trial-specific

medical history. In addition, trial-specific medical history will be summarised using reported term from the eCRF page (i.e. Diabetes Mellitus Type 1, Diabetes Mellitus Type 2, Diabetes Mellitus Other or Unknown, Arterial Hypertension, Hyperlipidaemia, Cardiac Dysrhythmias, Metabolic Syndrome).

A medication or non-drug therapy will be considered concomitant to treatment if either of the following applies:

- It is ongoing at the start of study treatment
- The start date occurs between the start of study treatment and 28 days after the end of study treatment inclusive.

A medication or non-drug therapy will be considered prior to treatment if the end date occurs before the start of study treatment.

Concomitant medication will be summarised descriptively by ATC3 class and preferred name. Prior medication will not be summarised.

Concomitant non-drug therapy will be summarised by SOC and PT. Prior non-drug therapy will not be summarised.

7.3 TREATMENT COMPLIANCE

Treatment compliance based on return of unused and empty syringes will not be analysed in this trial.

Any discrepancies between medication assigned, medication dispensed and medication taken will be assessed through the process for determining important protocol deviations (IPDs).

[Section 6.1.3](#) describes situations in which the actual maintenance treatment may not be the same as the planned (randomised) maintenance treatment. The CTP specifies rules for adjusting the Survodutide dose (or if necessary discontinuing the patient from treatment) depending on the number of missed doses and whether missed doses are consecutive. Therefore treatment compliance is directly related to the procedure for assigning Survodutide dose.

7.4 PRIMARY ENDPOINT(S)

Frequency tables will be produced of the primary endpoint (improvement in histological findings based on liver biopsy after 48 weeks of treatment, as defined in [Section 5.1](#)) in each of the following different ways:

- TS, actual maintenance treatment, using all post-baseline biopsy data (both on- and off-treatment as defined in [Section 6.1.6](#), and irrespective of timing relative to first dose of study treatment)
- TS, planned maintenance treatment, using all post-baseline biopsy data (as above)

- TS, actual maintenance treatment, using only on-treatment post-baseline biopsy data which are at least 280 days (40 weeks) after first dose of study treatment
- TS, planned maintenance treatment, using only on-treatment post-baseline biopsy data which are at least 280 days (40 weeks) after first dose of study treatment.

The above frequency tables will display the number and proportion of responders and non-responders respectively. Non-responders will be further split on these tables into those derived from the available data without imputation and those which were imputed due to a missing response.

7.4.1 Primary analysis of the primary endpoint(s)

The primary analysis of the primary endpoint will be performed on the TS using actual maintenance treatment, and using all post-baseline biopsy data (as above). Patients without post-baseline biopsy (whether this is expected or not) will be imputed as non-responders in this analysis.

A logistic regression will first be performed on the primary endpoint to estimate the treatment effects of multiple doses of Survodutide and placebo, together with the corresponding variance-covariance matrix. Applying the Multiple Comparison Procedures and Modelling (MCPMod) approach, these estimates will then be further used to test for a non-flat dose response curve and to identify suitable dose-response shapes out of a selection of candidate models.

The MCPMod approach [R10-1424, R15-4293] is implemented in two main steps: (1) trial design stage; (2) trial analysis stage. The procedures for the trial design stage, including the selection of candidate models covering a suitable range of dose-response shapes, are provided in the CTP Section 7.2.2. Additional details for the trial analysis stage are specified below.

Logistic regression

The responses for each dose group, as well as their variance-covariance matrix, for the primary endpoint will be estimated using a logistic regression (using a logit link via PROC LOGISTIC in SAS®). The logistic regression model will be fitted without an intercept, and will include presence of diabetes of any type [yes, no], baseline fibrosis score [F1, F2, F3] and the dose group as factors. In the case that 0 events are observed in any combination of dose group and strata, a penalized regression based on the Firth bias reduction method [R20-2291] will be used. The subsequent MCPMod analysis will be fully carried out on the logit scale, and the graphical displays of the fitted models in the Mod step will then be converted from the logit scale to the probability scale for interpretation reasons.

A summary table will be produced of the logistic regression results, including estimated odds ratios for the comparison of each Survodutide dose against placebo and their 95% confidence intervals and associated p-values.

MCPMod

The “DoseFinding” package [R15-2001] will be used for MCPMod analysis.

The multiple comparison procedure will be implemented using contrast tests which control the family-wise type I error rate at a one-sided $\alpha = 0.05$. Candidate models will be used as described in the CTP Section 7.2.2, that is:

- Linear
- Exponential1: 25% of maximum effect achieved at dose 3.0 mg (note: this dose is used for model specification only, it was not included in the trial)
- Exponential2: 5% of maximum effect achieved at dose 3.0 mg
- Emax1: 50% of maximum effect achieved at dose 3.0 mg
- Emax2: 80% of maximum effect achieved at dose 3.0 mg
- Quadratic: Maximum effect achieved at dose 4.8 mg.

For the MCPMod test, the contrast coefficients of each candidate model will be calculated using the R-function ‘optContr’ based on observed results from the logistic regression (with Firth bias reduction if used), that is, the variance-covariance matrix from the logistic regression step will be used as input to ‘optContr’.

If at least one dose-response model is statistically significant, the null hypothesis of a flat dose-response curve can be rejected indicating a benefit of Survodutide over placebo.

All dose-response models will be re-fitted to the data (irrespective of statistical significance in the previous step) without any parameter assumptions to generate a set of new estimates of the model parameters. For all significant models, the generalised Akaike Information Criterion (AIC) will be calculated and reported in the displays. The final model will be chosen as the model with the best fit according to AIC, that is, the model with the smallest AIC value.

The target dose for MCPMod purposes is defined as the smallest Survodutide dose which is estimated to achieve an absolute improvement in the proportion of patients with a histological improvement based on liver biopsy after 48 weeks of treatment of 20% or more compared with placebo. If no dose within the range studied by the trial meets this criterion, then it will be concluded that MCPMod has not identified a target dose.

Estimates for each dose group will be calculated and will be based on the final dose-response model. In practice, the choice of the target dose to be investigated in Phase 3 will be based upon efficacy as well as considering tolerability and safety and other relevant information.

The following tables and displays are planned:

- Table of the contrast coefficients per dose group and candidate model, together with the MCPMod test statistics and p-values for each model, and the critical value.
- For all models fitted to the observed data: Figure of the fitted dose-response curve plus 95% confidence band overlayed with adjusted mean and corresponding 95% confidence interval per dose (estimated from the logistic regression (with Firth bias reduction if used)) – this figure is plotted on the logit scale.
- For all models fitted to the observed data: Figure of the fitted dose-response curve plus 95% confidence band overlayed with adjusted mean and corresponding 95%

confidence interval per dose (estimated from the logistic regression (with Firth bias reduction if used)) – this figure is plotted on the probability scale (figure converted from logit-scale to probability scale).

The predicted Survodutide dose which achieved a 20% improvement in absolute responder proportions compared with placebo will be annotated onto the above figures on the probability scale for the significant model shapes (Linear, Exponential, Emax and Quadratic).

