**Footnotes for Flow Chart:**

1. Visit 1a is not required if a historical biopsy with sufficient and analysable material was collected within the last 6 months prior to randomisation (refer to [Section 3.3.1](#) and [5.1.1](#)).
2. Day of randomisation and the first administration of trial medication.
3. In case of early discontinuation (ED), Visit 32 should be completed instead of the planned treatment period visit, as soon as possible after trial medication is stopped. Liver biopsy should be performed at the ED visit providing the patient has been on treatment with trial medication for at least 40 weeks. MR imaging does not need to be performed at the ED visit if the patient discontinues before Visit 22 or if another MR imaging was performed within 12 weeks before the ED. [REDACTED] [REDACTED] [REDACTED] [REDACTED] Follow-up Visit 33 should be performed 4 weeks/28 days after the ED visit.
4. Number of weeks since randomization.
5. Trial visits will be conducted in two ways: 1/ at site (indicated by “S” in the [Flow Chart](#)) and 2/ remotely via telemedicine from patient’s home (indicated by “T” in the Flow Chart). Method of visit conduct (on-site or remote) can be modified. Modifications from an on-site to a remote visit require Sponsor approval.
6. Visit 1 can be conducted within less than 10 weeks of randomization. Before randomization, the Investigator should ensure that all safety laboratory results, ECG reading, imaging and liver biopsy results are available to ensure that the patient meets all inclusion criteria and does not meet any exclusion criteria. In the event of logistical issues with the reporting of results by the central vendor(s) a patient who meets all inclusion criteria and does not meet any exclusion criteria should be considered for participation in the clinical trial even if he/ she exceeds the screening period of 10 weeks. Extension of the screening period requires a Sponsor approval. If more than 12 weeks elapse from Visit 1 safety laboratory tests, ECG and vital signs should be repeated and results should be available before randomization.
7. Patient must be informed and written informed consent must be obtained prior to starting any trial procedure. Fasting is considered part of a trial procedure. For the historical biopsy, if applicable, a written non-trial specific informed consent has been obtained (per local standard).
8. Physical examination after screening is required only if patient reports symptoms.

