#### Dose escalation period

During the dose escalation period a dose adjustment may only occur at Visit 16, 18, 20, 22 and 24. If a patient experiences tolerance issues with a dose due to AEs over the last two weeks before a remote visit (i.e., Visit 16, 20 or 24) and believes that a dose adjustment is needed, the patient will be asked to come to the site and to return the unused trial medication dispensed to him/ her during the previous site visit. The Investigator will assess together with the patient, if a dose adjustment is needed, and a new trial medication will be dispensed to the patient for the next two administrations.

If a patient experiences tolerance issues with a dose due to AEs over two weeks within the treatment period before Visit 14, the trial medication should be discontinued, and the patient should undergo the procedures of the EOT and Follow-up visit (Visit 32 and 33 resp.).

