#### 4.1.4 Drug assignment and administration of doses for each patient

Table 4.1.4: 1 shows the dose escalation scheme within each dose group.

Table 4.1.4: 1 Dose escalation schemes

Target dose	Visit											
	2	3	4	5	6	7	8	9	10	11	12	13
	Weeks on treatment											
	1	2	3	4	5	6	7	8	9	10	11	
Weekly dose (in mg)												
2.4 mg	0.3	0.3	0.6	0.6	0.9	0.9	1.2	1.2	1.8	1.8	1.8	1.8
4.8 mg	0.3	0.3	0.6	0.6	0.9	0.9	1.2	1.2	1.8	1.8	2.4	2.4
6.0 mg	0.3	0.3	0.6	0.6	0.9	0.9	1.2	1.2	1.8	1.8	2.4	2.4

Target dose	Visit											
	14	15	16	17	18	19	20	21	22	23	24	25
	Weeks on treatment											
	12	13	14	15	16	17	18	19	20	21	22	23
Weekly dose (in mg)												
2.4 mg	2.1	2.1	2.4	2.4	2.4	2.4	2.4	2.4	2.4	2.4	2.4	2.4
4.8 mg	3.0	3.0	3.6	3.6	4.2	4.2	4.8	4.8	4.8	4.8	4.8	4.8
6.0 mg	3.0	3.0	3.6	3.6	4.2	4.2	4.8	4.8	5.4	5.4	6.0	6.0

BI 456906 or placebo will be provided in pre-filled syringes. Each patient will be administered two injections at every dosing day. Trial medication will be administered preferably by a qualified site personnel during site visits. During remote visits and between site visits during the maintenance period trial medication will be administered by the patient or a designated person. Patient and a designated person (if appointed) will be properly trained before starting the administration at home. Furthermore, during remote visits the administration of trial medication will be monitored by a qualified site personnel via the video conferencing function available on the Science 37 platform. If the patient is not willing to self-administer the injections, he/ she should be given the option to visit the site and to have the medication administered by a qualified site personnel.

“Instructions for Use” (IFU) with step-by-step instructions on how to use the pre-filled syringe will be provided to each patient. A copy of the IFU will be placed in the ISF. The IFU will also contain important safety information and storage instructions. The injection site should be the abdomen, as shown in the instructions. Each dose (both pre-filled syringes) should be administered on one side of the abdomen, and the next dose should be administered on the alternate side of the abdomen.

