## **7.2.2 Primary endpoint analyses**

The primary analysis of the primary endpoint will be performed using multiple comparison and modelling techniques (MCPMod), whereby several possible dose response models (patterns) will be evaluated while keeping full control of the type I error at 5% (one-sided), to identify the best-fitting model or subset of models.

[figure not shown]
A logistic regression analysis will first be carried out on the primary endpoint. Covariate-adjusted estimates of the log odds for each dose and the covariance matrix will be extracted from the logistic regression fit and used for the subsequent MCPMod analysis. The MCPMod analysis will be carried out on the logit scale, and the results converted back to the original response scale for interpretation. The logistic regression model will be fitted without an intercept and will include presence of diabetes of any type (yes, no) and baseline fibrosis stage (F1, F2, F3), as well as the dose group, as factors.

The basic shape of each of the models to be tested must be pre-defined. The following model assumptions and resulting graphs ([Figure 7.2.2: 1](#)) have been selected to cover a plausible and

diverse range of dose response patterns, with placebo response rate assumed to be 20% [[R16-5487](#); [R16-5489](#); [R18-2781](#)] and maximum BI 456906 response rate assumed to be 45%. The maximum BI 456906 response rate occurs at the highest BI 456906 dose under monotone assumptions; one non-monotone dose response pattern is also included here, to allow for the possibility that this is not the case. Note: specifications here are made on the original response scale, but the MCPMod analysis itself must use the logit scale, i.e., in which the assumed placebo response rate is  $\log(0.20/(1-0.20))$  and the maximum BI 456906 response rate is  $\log(0.45/(1-0.45))$ :

- Linear
- Exponential1: 25% of maximum effect achieved at dose 3.0 mg (Note: a 3.0 mg dose is only used to specify the models here and below. This dose is not proposed for inclusion in the trial.)
- Exponential2: 5% of maximum effect achieved at dose 3.0 mg
- Emax1: 50% of maximum effect achieved at dose 3.0 mg
- Emax2: 80% of maximum effect achieved at dose 3.0 mg
- Quadratic: Maximum effect achieved at dose 4.8 mg.

Figure 7.2.2: 1 Dose response patterns considered for the MCPMod analysis of the primary endpoint

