6.1.3 Actual Maintenance Treatment Group

According to the rules for escalating and adjusting the Survodutide dose given in the CTP, it is envisaged that some patients may not receive the planned maintenance treatment according to the randomised treatment group, whilst nevertheless remaining on treatment.

Actual maintenance treatment group will be defined for analysis as follows:

- If the patient started the maintenance period, then actual maintenance treatment group will be defined in all circumstances to be the dose at the start of the maintenance period (which is expected to be one of the Survodutide maintenance doses), regardless of whether previous dose escalation was performed in the expected way according to the protocol. This includes each of the following situations:
 - Any patient who successfully reached their planned maintenance dose at the end of the dose escalation period
 - Any patient who did not reach their planned maintenance dose at the end of the dose escalation period, and who only reached a lower maintenance dose
 - Any patient for whom the start and end maintenance dose are not the same, regardless of whether the patient started the maintenance period on their planned maintenance dose, and regardless of whether the permanent dose reduction was planned according to the protocol, or whether it was unplanned (e.g. where the wrong tolerability information was given to the IRT and the dose was not re-escalated back to correct the error).
- If the patient discontinued treatment during the dose escalation period, actual maintenance treatment group will be defined as the next planned maintenance dose up from the dose at discontinuation. The same rule will be applied irrespective of the reason for discontinuing treatment during the dose escalation period, and will be applied irrespective of whether the dose prior to the dose at discontinuation was as anticipated from the protocol dose escalation strategy.

Table 6.1.3: 1 Definition of actual maintenance treatment group for patients randomised to active Survodutide maintenance treatment who discontinued treatment during the dose escalation period

| Dose at discontinuation | Actual maintenance treatment group |
|---|------------------------------------|
| Dose = 0 mg | Placebo |
| $0.3 \text{ mg} \leq \text{Dose} \leq 2.4 \text{ mg}$ | 2.4 mg |
| $2.4 \text{ mg} < \text{Dose} \leq 4.8 \text{ mg}$ | 4.8 mg |
| Dose > 4.8 mg | 6.0 mg |

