- All patients randomised to placebo maintenance treatment or who were switched to placebo during the dose escalation period will be assigned to placebo for actual maintenance treatment group.

For the purposes of display in outputs, “actual treatment” means the same as “actual maintenance treatment”.

The above rules cover all known and anticipated situations. The possibility of other situations which are not anticipated from the protocol, and which cannot be identified from blinded data, cannot however entirely be excluded. A review of unblinded dosing data will be performed immediately after unblinding the database at DBL, to identify any dosing situation for which the above TSAP rules might not be adequate. Such situations might include, but not necessarily be limited to, unexpected increases in maintenance dose, or starting Survodutide maintenance doses which are not one of 2.4 mg, 4.8 mg or 6.0 mg. An attempt will be made to find out whether data error or omission is the explanation, or whether a real issue actually occurred in any such patients. Any additional decisions required on assigning actual maintenance treatment at that time will be documented in the CTR.

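### Grouping the primary MCPMod by actual dose moves imputed failures out of the higher doses into 2.4 mg, so with escalation drop-out the 5% error claim fails and the 6.0 mg effect is inflated

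*SAP*

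**What the plan says.** SAP 7.4.1 sets the grouping: "The primary analysis of the primary endpoint will be performed on the TS using actual maintenance treatment". For patients who stop during escalation, SAP 6.1.3 adds: "actual maintenance treatment group will be defined as the next planned maintenance dose up from the dose at discontinuation". Its Table 6.1.3:1 gives the bands for patients randomised to active treatment. A dose of 0.3 to 2.4 mg at stopping is analysed as 2.4 mg, above 2.4 and up to 4.8 mg as 4.8 mg, and above 4.8 mg as 6.0 mg. Neither the active arm nor the reason for stopping matters. Placebo is treated differently: "All patients randomised to placebo maintenance treatment or who were switched to placebo during the dose escalation period will be assigned to placebo".

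Two other rules fix the outcome of these patients. Flow chart footnote 3 in the protocol says: "Liver biopsy should be performed at the ED visit providing the patient has been on treatment with trial medication for at least 40 weeks". SAP 7.4.1 says: "Patients without post-baseline biopsy (whether this is expected or not) will be imputed as non-responders in this analysis". Protocol 4.1.2 adds, for early intolerance: "experiences tolerance issues with a dose due to AEs over two weeks within the treatment period before Visit 14, the trial medication should be discontinued". In protocol Table 4.1.4:1 every scheduled dose up to Visit 13 is 2.4 mg or less in all active arms.

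On error control, protocol 7.2.2 says the candidate models will be "evaluated while keeping full control of the type I error at 5% (one-sided"). SAP 7.4.1 repeats family-wise control at one-sided 0.05. Protocol 7.5 puts the chance of a false decision for an ineffective drug below 1% at a delta of 20% and below 5% at a delta of 10%. The SAP target dose is the smallest dose with a modelled gain over placebo of at least 20 points. MCPMod by planned (randomised) dose is a sensitivity analysis only (protocol 7.2.2, SAP 7.4.2).

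**The concern.** The analysis group depends on something that happens after randomisation and that all but determines the endpoint. A patient randomised to 4.8 or 6.0 mg who stops early is a non-responder by imputation and is then counted against 2.4 mg. A placebo patient who stops at the same week is counted against placebo. The rule therefore cleans failures out of the top doses and lowers 2.4 mg, and this alone produces a rising curve.

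Two things are at stake. The primary test can reject when the randomised arms have identical response rates. The 6.0 mg minus placebo difference, which feeds the 20-point target-dose rule for Phase 3, comes out too large. Protocol 7.5 does consider unequal as-treated group sizes, but only with a real effect (20% vs 45%) and with independent binomial draws per group. It never examines the null with moved patients as failures.

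**Working it through.** **Inputs from the documents.** 60 per arm; placebo 20%, maximum 45%; one-sided 5%; six candidate shapes (protocol 7.2.2); delta 20% or 10% (protocol 7.5); dose schedule (Table 4.1.4:1); bands (SAP Table 6.1.3:1).

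**Assumed.** Escalation drop-out d of 5% to 20%, equal in all arms unless stated. Timing (a): stops spread evenly over 24 weeks. Timing (b): all stops before Visit 14.

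**Where drop-outs go.** Under (a), 12 of 24 dosing weeks are at 2.4 mg or below, so 50% of 4.8 mg-arm stops move to 2.4 mg and the rest stay. For the 6.0 mg arm, 12/24 = 50% move to 2.4 mg, 8/24 = 33% move to 4.8 mg and 4/24 = 17% stay. Under (b), all move to 2.4 mg.

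**Hand check, flat null, d = 20%.** The completer rate is 20%/(1 − 0.20) = 25%, so each arm has 48 × 0.25 = 12 responders of 60.

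| Group | By randomised dose | As analysed, (a) | As analysed, (b) |
|---|---|---|---|
| Placebo | 12/60 = 20% | 12/60 = 20% | 12/60 = 20% |
| 2.4 mg | 12/60 = 20% | 12/(60+6+6) = 16.7% | 12/(60+12+12) = 14.3% |
| 4.8 mg | 12/60 = 20% | 12/(60−6+4) = 20.7% | 12/48 = 25.0% |
| 6.0 mg | 12/60 = 20% | 12/(60−6−4) = 24.0% | 12/48 = 25.0% |

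**Simulation.** Logit estimates per group; optimal contrasts from the estimated covariance; multivariate-normal critical value (1.956 when balanced); refit; smallest generalised AIC among significant models; maximum modelled effect over 0–6 mg, on the probability scale, compared with delta. Shape parameters: Emax ED50 3.0 and 3.0 × 0.2/0.8 = 0.75; exponential 3/ln 3 = 2.73 and 3/ln 19 = 1.02; quadratic peak at 4.8 mg; linear. No covariates; 20,000 runs per scenario; Monte Carlo SE at most 0.4 points.

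**Reproducing Table 7.5:1** (positive test / success at delta 20%):

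| Placebo vs high dose | Simulated | Stated |
|---|---|---|
| 20% vs 45% | 92.6% / 77.6% | 92.1% / 75.9% |
| 20% vs 25% | 15.8% / 2.7% | 15.6% / 2.2% |
| 20% vs 20% | 4.7% / 0.4% | 4.5% / 0.2% |

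The model-fitting step runs slightly high (by up to 1.7 points with a real effect and 0.2 under the null).

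**Flat null: randomised arms exactly 20%.**

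| Drop-out | As-treated rejection, (a) / (b) | False success at delta 20%, (a) / (b) |
|---|---|---|
| 5% | 6.4% / 7.8% | 0.6% / 0.7% |
| 10% | 8.5% / 12.3% | 0.9% / 1.4% |
| 15% | 11.9% / 19.0% | 1.5% / 3.3% |
| 20% | 15.9% / 28.1% | 2.6% / 6.7% |

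By randomised dose, rejection is 4.4% to 4.9% throughout. At delta 10%, false success equals the rejection rate (6.4% to 28.1%, against the stated limit of 5%). Recoded from scratch, timing (b) gives 7.3%, 12.1%, 18.7% and 27.3%. If every stop comes from Visit 14 onward, the flat-null rejection rate is still 5.5%, 6.0% and 8.1% at 5%, 10% and 20% drop-out.

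**Step-downs are not the cause.** Let 10% of each active arm step down, stay on treatment and be biopsied (2.4 mg to placebo; 4.8 and 6.0 mg to 2.4 mg). Rejection is 5.0% to 5.2% with no drop-out, 7.9% / 11.7% at 10% and 13.1% / 23.9% at 20%.

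**The protocol's own splits under the null** (completers at 20%), in the order 60/60/70/50, 60/70/70/40, 60/80/50/50, 60/90/50/40: 3.8%, 4.8%, 7.8%, 10.0% if all moved patients are non-responders; 4.0%, 4.5%, 6.1%, 6.5% if half are; 4.6% to 4.8% if none are. Only the two splits that move patients solely into 2.4 mg inflate the error.

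**Effect on 6.0 mg.** With a true randomised difference of 15 points (35% vs 20%), 35% is 21 of 60. At 20% drop-out this becomes 21/50 = 42% under (a) or 21/48 = 44% under (b).

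| True difference | Drop-out | As-treated difference, (a) / (b) | P(success, delta 20%), (a) / (b) |
|---|---|---|---|
| 15 points | 10% | 18 / 19 | 45% / 56% |
| 15 points | 20% | 22 / 24 | 66% / 84% |
| 25 points | 10% | 29 / 30 | – |
| 25 points | 20% | 34 / 36 | – |

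By randomised dose, P(success) for the 15-point case is 28% to 29%.

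**The case against.** The size depends on assumptions the documents do not supply. Intolerance should cause more stopping on active drug than on placebo, whereas the main table assumes equal drop-out. With completers at 20% in every arm, 20% active and 10% placebo drop-out and 5% later stops, rejection falls to 9.0% / 16.1% and false success at delta 20% to 0.7% / 1.7%. With placebo drop-out of 0% or 5%, active drop-out of 10% to 20% and all stops from Visit 14 onward, rejection is 3.1% to 4.6%. The stated limit of 1% also survives at 5% drop-out, and at 10% with even timing. All of this stands as a limit on size. In those settings, however, the active arms respond less than placebo by randomised dose (15% vs 17% in the 9.0% / 16.1% case), so they are not the flat null at which a type I error claim must hold.

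The trial is also declared exploratory (protocol 7.1), the as-treated grouping is openly stated, and Phase 3 dose choice will weigh safety and tolerability. SAP 7.4 tabulates responders by both groupings with imputed non-responders shown separately. SAP section 7 plans a planned-versus-actual shift table, and SAP 7.4.2 repeats MCPMod by planned dose. These outputs would let a reader see the movement. They do not make the primary test a 5% test or correct the curve from which the target dose is read. The control statements in protocol 7.2.2 and SAP 7.4.1 could be read as covering multiplicity across the six shapes only. The limits in protocol 7.5 cannot be read that way: they concern an ineffective drug. Protocol 1.3 also gives the trial a confirmatory role alongside the pivotal trial. Further sensitivity text is redacted and cannot be judged.

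**Conclusion.** The concern holds. The mechanism follows directly from the written rules. With randomised arms flat at 20%, the as-treated test exceeds 5% at every drop-out rate examined from 5% upward: 6.4% to 7.8% at 5% drop-out, rising to 15.9% to 28.1% at 20%. By randomised dose it stays below 5%. The 6.0 mg difference is inflated by 3 to 5 points at 10% drop-out and 7 to 11 points at 20%, for true differences of 15 to 25 points. The mechanism is certain. The size is conditional on assumed rates and timing, on equal drop-out across arms and on a model without covariates, and it is smaller when stops come late or placebo drop-out is low. A biopsy taken unexpectedly early would be used, and patients switched to placebo are grouped with placebo; both are minor exceptions.

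**What to change.** Make the planned-dose MCPMod in SAP 7.4.2 the primary analysis and the basis of the 20-point target-dose rule. Keep the actual-dose analysis as supportive, with patients who discontinue during escalation left in their randomised arm. At minimum, confine the type I error statements in protocol 7.2.2 and SAP 7.4.1 to the planned-dose analysis. In protocol 7.5, either say that the false-positive figures (below 1%, below 5%, and the null rows of Table 7.5:1) do not apply to the as-treated analysis, or re-simulate them with escalation drop-outs imputed as non-responders and moved as SAP 6.1.3 directs.

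The cost is wording, since the analysis is already specified. The primary curve will be shallower if drop-out is material. The SAP is at version 2.0 and a sponsor-run unblinded interim has taken place, so a change of primary grouping needs its reason given and must be documented as made before final unblinding.
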